#### ***7.3.4 Follow-Up***

Participants will be instructed to attend the Clinilabs facility to continue study procedures as per the protocol time points outlined in Table 7-1. There are allowable variations in actual day of collection as long as the variation is recorded. At these time points, PK blood will be collected along with an injection Site assessment where applicable, PHQ-9 & BDI-II, concomitant medication review and AE monitoring.

#### ***7.3.5 Final Study Visit***

All participants will be required to attend the Clinilabs study site for a final visit with a study clinician as outlined in Table 7-1.

Participants will be monitored for the following: AEs, PHQ-9, BDI-II, CSSRS, concomitant medication review, Vital signs, substance Use (Self report) and UDS.

#### ***7.3.6 Early Termination Visit***

Any participants that are withdrawn will be requested to attend Clinilabs for an early termination /withdrawal visit as outlined in Table 7-1. Participants will be advised of their option as outlined in section 5.4.2.

A follow-up visit may be conducted 30 days after the last scheduled on-study visit and is required only if a participant has ongoing AEs or laboratory abnormalities at the last on-study visit. An in-clinic follow-up visit must be conducted 30 days after the last scheduled on-study visit for an AE requiring laboratory testing for participants with the following conditions at the last on-study visit: ongoing AEs, SAEs regardless of attributability, any laboratory abnormalities considered to be AEs or potentially harmful to the participant. For in-clinic follow-up visits, assessments performed should reflect what is considered medically necessary to assess the event(s).

#### ***7.3.7 Unscheduled/Late Visits***

It is anticipated that some participants may miss or be delayed to some of their appointments. Every effort will be made to obtain blood samples at the scheduled dates, but blood samples will be accepted if they are taken late, with allowances made in the statistical analysis. Participants who miss appointments will be contacted by phone to encourage them to return

for as many appointments as possible. However, some dropouts are also anticipated so additional participants have been recruited to aim for a total of 4 completers.

Participants will be asked to complete the following as a minimum; concomitant medication review, Vital signs, PK blood collection and AE monitoring.

#### ***7.3.8 AE Follow-up Visit***

A follow-up visit will be conducted 30 days after the last scheduled on-study visit. This visit is required only if a participant has ongoing AEs or laboratory abnormalities at the last on-study visit. An in-clinic follow-up visit must be conducted 30 days after the last scheduled on-study visit for an AE requiring laboratory testing for participants with the following conditions at the last on-study visit: ongoing AEs, SAEs regardless of attributability, any laboratory abnormalities considered to be AEs or potentially harmful to the participant. For in-clinic follow-up visits, assessments performed should reflect what is considered medically necessary to assess the event(s).

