## 7.3.9 Assessment Time Point Table

Table 7-1: Assessment Time Points

Visit description	Demographics, Medical/psychiatric history review	Physical & Mental Status exam, ECG	Concomitant medication review	PHQ-9, BDI & CSSRS 	Informed consent	LFT, EUC & FBE blood collection	Pregnancy test 	Adverse Event Monitoring 	Substance Use: Self report & UDS	Vital signs	NCT & COWS 	PK Blood collection 	Vivitrol administration 
Screening visit	X	X	X	X	X	X	X	X	X	X	X		
Recruitment			X		X			X		X			
Admission Day 0, 1, and 2			X	X			X	X	X	X	X	X	X
Day 3, 5, 7, 10, 14, 17, 21 & 24 ( $\pm$ 1 day)			X	X			X			X		X	
Day 28, 56, 84 & 112 ( $\pm$ 1 day)			X	X		X	X	X	X	X		X	X
Admission Day 140, 141, and 142			X	X		X	X	X	X	X		X	X
143 days $\pm$ 6hr			X					X		X		X	
Day 145, 147, 150, 154, 157, 161, 164, 168 ( $\pm$ 1 day)			X	X			X	X	X	X		X	
Day 182 ( $\pm$ 2 day)			X	X				X		X		X	
Day 196 (Final Visit) ( $\pm$ 2 day)			X	X	X	X		X	X	X		X	
Early Termination			X	X	X	X		X	X	X		X	
Unscheduled/Late visit			X	X				X		X		X	
AE Follow-up			X	X		X		X		X			

1. CSSR-S Lifetime will be completed at screening, C-SSRS will be used to assess suicidal risk since the last visit.
2. Pregnancy testing will be conducted on all females on serum during screening and will be continued with urine testing monthly afterwards.
3. AE follow-up visit may be conducted 30 days after the final study visit and is required only if a participant has ongoing AEs or laboratory abnormalities.
4. NCT/COWS will be done during Day 0

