### **8.3 TIME PERIOD AND FREQUENCY FOR EVENT ASSESSMENT AND FOLLOW-UP**

The occurrence of an AE or SAE may come to the attention of study personnel during study visits and interviews of a study participant presenting for medical care, or upon review by a study monitor.

All AEs including local and systemic reactions not meeting the criteria for SAEs will be captured on the appropriate CRF. Information to be collected includes event description, time of onset, clinician's assessment of severity, relationship to study product (assessed only by those with the training and authority to make a diagnosis), and time of resolution/stabilization of the event. All AEs occurring while on study must be documented appropriately regardless of relationship. All AEs will be followed to adequate resolution.

Any medical condition that is present at the time that the participant is screened will be considered as baseline and not reported as an AE. However, if the study participant's condition deteriorates at any time during the study, it will be recorded as an AE.

Changes in the severity of an AE will be documented to allow an assessment of the duration of the event at each level of severity to be performed. AEs characterized as intermittent require documentation of onset and duration of each episode.

The PI will record all reportable events (as defined in 8.4) with start dates occurring any time after informed consent is obtained until 7 (for non-serious AEs) or 30 days (for SAEs) after the last day of study participation. At each study visit, the investigator will inquire about the occurrence of AE/SAEs since the last visit. Events will be followed for outcome information until resolution or stabilization.

In the event of study discontinuation for any reason, any ongoing AEs will be followed until resolution or until deemed stable by the PI, or until the participant is deemed by the PI to be lost to follow-up. If, in the opinion of the PI, it is necessary to monitor a participant beyond the safety follow-up visit, the follow-up period may be extended as necessary. In such instances, the Sponsor and the PI will agree to an acceptable follow-up schedule. The PI must maintain a record of all participants who fail to complete the study. The reason for study discontinuation will be made on the appropriate CRF.

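### No contact is scheduled in the 7-day AE and 30-day SAE windows after participation for anyone with nothing ongoing at the last visit, so new late events there depend on unsolicited reports

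*Combined protocol and SAP*

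**What the plan says.** Section 8.3 requires the investigator to record reportable events that start at any time from consent "until 7 (for non-serious AEs) or 30 days (for SAEs) after the last day of study participation". The same paragraph ties active enquiry to visits: "At each study visit, the investigator will inquire about the occurrence of AE/SAEs since the last visit".

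In Table 7-1 the last visit scheduled for every continuing participant is Day 196 (±2 days). Those who leave early are asked to attend an early-termination visit. The only planned contact after either is the AE follow-up, described in three places:

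- Section 7.3.8 opens with "A follow-up visit will be conducted 30 days after the last scheduled on-study visit" and then narrows it: "This visit is required only if a participant has ongoing AEs or laboratory abnormalities at the last on-study visit".
- Section 7.3.6, for participants who are withdrawn: "A follow-up visit may be conducted 30 days after the last scheduled on-study visit and is required only if a participant has ongoing AEs".
- Table 7-1, footnote 3: "AE follow-up visit may be conducted 30 days after the final study visit and is required only if a participant has ongoing AEs".

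Where the follow-up must take place in clinic, the trigger is again the participant's state at the last on-study visit: "ongoing AEs, SAEs regardless of attributability, any laboratory abnormalities considered to be AEs or potentially harmful to the participant".

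Section 8.1.1 names telephone interviews as one source of AEs, but no call is scheduled after the final or early-termination visit. The telephone contact in Section 5.3.3 serves to confirm and reschedule visits.

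**The concern.** The plan sets a period in which new events count but schedules no enquiry during it for participants who finish or leave with nothing ongoing. The follow-up rule looks back at events already known on the last visit, whereas the recording rule looks forward to events that have not yet begun. A participant who is well at the last visit and has an SAE two weeks later meets the recording rule but not the follow-up rule.

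Active ascertainment in the window therefore depends on having had an earlier event. Incidence of deaths, SAEs and other AEs is a declared safety endpoint (Section 4.2.2), and Section 10.4.5 reports treatment-emergent events as numbers and percentages of participants. Nothing in Sections 10.4.4 or 10.4.5 lets a reader tell a participant who was asked and had no event from one who was not asked.

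**Working it through.** The plan gives no figure for this point, so there is none to reproduce. The check is a timeline, followed by a comparison of who is contacted.

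**Inputs**

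- Last dose: Day 140 (Section 7.3.3.4)
- Final visit: Day 196, ±2 days (Table 7-1)
- Dosing interval: 28 days
- Recording windows: 7 days for non-serious AEs and 30 days for SAEs (Section 8.3)
- Stated safety period: 196 days (Section 3.2)
- Participants: up to 15 (Sections 4.1 and 5.3.1). The Protocol Summary still says up to 6. I use 15, the larger figure and the stated purpose of version 0.5.

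**Completers**

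- End of AE window: 196 + 7 = Day 203 (201 to 205 with the ±2 days)
- End of SAE window: 196 + 30 = Day 226 (224 to 228)
- Share of the recording period, counted from Day 0, with no scheduled contact if nothing is ongoing: 7/203 = 3.4% for AEs and 30/226 = 13.3% for SAEs
- Last dose to final visit: 196 − 140 = 56 days, or two dosing intervals
- Last dose to end of window: 203 − 140 = 63 days for AEs and 226 − 140 = 86 days for SAEs

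Both windows open when the stated safety period closes.

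**Early leavers.** Let the termination visit be on Day T, d days after the most recent dose.

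- The SAE window ends on Day T + 30. It lies wholly inside the 196 days when T ≤ 196 − 30 = 166.
- The AE window ends on Day T + 7. It lies wholly inside when T ≤ 196 − 7 = 189.
- For d from 0 to 28, the AE window ends d + 7 = 7 to 35 days after that dose, and the SAE window ends d + 30 = 30 to 58 days after it.

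Example: a participant who leaves on Day 60 is 4 days past the Day 56 dose. The SAE window runs to Day 90, all of it within the safety period, and ends 34 days after that dose. Section 2.3.1 puts the duration of blockade at about 28 days, and Section 5.4.2.1 notes that the injection cannot be removed.

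**Who is contacted in the window**

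| State at final or termination visit | Scheduled contact | Routes for a new event |
|---|---|---|
| AE or laboratory abnormality ongoing | Follow-up required at 30 days | Direct enquiry, plus unsolicited reports |
| Nothing ongoing | None required; visit allowed | Unsolicited reports only, unless the optional visit is held |

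**Upper bound.** If nobody had anything ongoing, the time without scheduled contact would be 15 × 7 = 105 person-days for AEs and 15 × 30 = 450 for SAEs. The documents give no rate of ongoing events, so I put no figure on the number actually affected.

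**Undefined anchor.** Section 8.3 does not define the last day of study participation. If the Day 226 follow-up visit counts as participation, the windows move to 226 + 7 = Day 233 and 226 + 30 = Day 256, and again no contact is scheduled in them.

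**The case against.** The strongest defence is that Section 8.3 states what must be recorded if it becomes known and does not promise active enquiry throughout the window. A reporting window paired with conditional follow-up is then a design choice, and there is no contradiction. That stands, and I do not call this an inconsistency. It leaves the uneven ascertainment in place.

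The second defence is that the safety objective covers 196 days, AE monitoring runs to Day 196, and completers are by then 56 days past the last dose. The study has one arm and no stated hypothesis, so uneven late ascertainment cannot bias a comparison between groups. For completers this largely disposes of the point. It does not for most early leavers, whose window falls inside the 196 days.

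Third, early leavers are partly covered. They are asked to attend a termination visit with AE monitoring and laboratory tests, and ongoing AEs are followed to resolution or stability. Those who withdraw may also refuse further contact (Section 5.4.2.1), which limits any remedy in the group that matters most. All of this is true, but none of it reaches events that begin after the visit.

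Three stronger readings are tempting, and the documents do not support them.

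- A reader might infer that late events in the other participants are impossible to capture. Sections 7.3.6 and Table 7-1 allow the visit for anyone, Section 8.1.1 names telephone interviews, and Section 8.3 accepts events found when a participant presents for care or on monitor review.
- A reader might infer that an unobserved window is counted as event-free. No passage says so: Sections 10.4.4 and 10.4.5 deal only with recorded events.
- A reader might take the 3 of 15 not expected to complete (15 − 12) as the number leaving early. Section 5.3.1 defines completion by valid PK samples, so a participant can attend to Day 196 and still not be a completer.

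The consent pages were removed before review. They may tell participants how to report late events, which cannot be checked here.

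**Conclusion.** The point holds in a limited form and is minor. For participants with nothing ongoing at the final or early-termination visit, no contact is scheduled in the window in which Section 8.3 says new events count. Enquiry there is assured only for those who already had an event.

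For completers the uncovered stretch is 3.4% of the AE recording period and 13.3% of the SAE recording period. It falls after the stated safety period and at least two dosing intervals after the last dose, so little is at stake. For early leavers it can fall within the safety period and soon after a dose. As an illustration, if 15 are dosed, one unreported SAE in such a window would change SAE incidence by 1/15, or 6.7 percentage points.

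This rests on reading the last day of participation as the final or early-termination visit, and on the optional visit not being held routinely. The documents say neither how many participants will leave early nor how many will have something ongoing, so the number affected cannot be estimated from them.

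**What to change.** - **Sections 7.3.6 and 7.3.8, and Table 7-1 footnote 3:** add one scripted telephone AE/SAE enquiry 30 days after the final or early-termination visit, for every dosed participant who has not refused further contact. It should ask separately about non-serious events in the first 7 days and SAEs over the full 30 days. The in-clinic visit stays conditional as now.
- **Section 8.3:** define the last day of study participation as the final or early-termination visit, so that the windows do not move when a follow-up visit is held.
- **Sections 10.4.4 and 10.4.5:** report how many dosed participants were reached for the post-participation window, alongside the events found in it.

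For completers, a call at about Day 226 covers both windows (Days 203 and 226). For early leavers, the call falls on Day T + 30 and does the same.

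The cost is at most 15 short calls, which existing staff could make, a small wording change and one extra line in the safety tables. Participants who refuse contact or cannot be reached will still be unobserved in the window, but the report will show how many there are. No dosing or clinical rule changes.

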## 7.3.9 Assessment Time Point Table

Table 7-1: Assessment Time Points

Visit description	Demographics, Medical/psychiatric history review	Physical & Mental Status exam, ECG	Concomitant medication review	PHQ-9, BDI & CSSRS 	Informed consent	LFT, EUC & FBE blood collection	Pregnancy test 	Adverse Event Monitoring 	Substance Use: Self report & UDS	Vital signs	NCT & COWS 	PK Blood collection 	Vivitrol administration 
Screening visit	X	X	X	X	X	X	X	X	X	X	X		
Recruitment			X		X			X		X			
Admission Day 0, 1, and 2			X	X			X	X	X	X	X	X	X
Day 3, 5, 7, 10, 14, 17, 21 & 24 ( $\pm$ 1 day)			X	X			X			X		X	
Day 28, 56, 84 & 112 ( $\pm$ 1 day)			X	X		X	X	X	X	X		X	X
Admission Day 140, 141, and 142			X	X		X	X	X	X	X		X	X
143 days $\pm$ 6hr			X					X		X		X	
Day 145, 147, 150, 154, 157, 161, 164, 168 ( $\pm$ 1 day)			X	X			X	X	X	X		X	
Day 182 ( $\pm$ 2 day)			X	X				X		X		X	
Day 196 (Final Visit) ( $\pm$ 2 day)			X	X	X	X		X	X	X		X	
Early Termination			X	X	X	X		X	X	X		X	
Unscheduled/Late visit			X	X				X		X		X	
AE Follow-up			X	X		X		X		X			

1. CSSR-S Lifetime will be completed at screening, C-SSRS will be used to assess suicidal risk since the last visit.
2. Pregnancy testing will be conducted on all females on serum during screening and will be continued with urine testing monthly afterwards.
3. AE follow-up visit may be conducted 30 days after the final study visit and is required only if a participant has ongoing AEs or laboratory abnormalities.
4. NCT/COWS will be done during Day 0
5. PK Collection to be performed at: 1hr  $\pm$  15min, 2hr  $\pm$  15min, 4hr  $\pm$  30min, 8hr  $\pm$  60min, 12hr  $\pm$  60min, 24hr  $\pm$  2hr (day 1), 1.5 days  $\pm$  2hr, 1.75 days  $\pm$  2hr, 2days  $\pm$  2hr, 3 days  $\pm$  6hr, 5 days  $\pm$  1 day, 7 days  $\pm$  1 day, 10 days  $\pm$  1 day, 14 days  $\pm$  1 day, 17days  $\pm$  1 day, 21 days  $\pm$  1 day, 24 days  $\pm$  1 day, 28 days  $\pm$  1 day sample before redose, 56 days  $\pm$  1 day sample before redose, 84 days  $\pm$  1 day sample before redose, 112 days  $\pm$  1 day sample before redose, 140 days  $\pm$  1 day sample before redose, 140 days + 1hr  $\pm$  15min, 140 days + 2hr  $\pm$  15min, 140 days + 4hr  $\pm$  30min, 140 days + 8hr  $\pm$  60min, 140 days + 12hr  $\pm$  60min, 141 days  $\pm$  2hr, 141.5 days  $\pm$  2hr, 141.75 days  $\pm$  2hr, 142 days  $\pm$  2hr, 143 days  $\pm$  6hr, 145 days  $\pm$  1 day, 147 days  $\pm$  1 day, 150 days  $\pm$  1 day, 154 days  $\pm$  1 day, 157 days  $\pm$  1 day, 161 days  $\pm$  1 day, 164 days  $\pm$  1 day, 168 days  $\pm$  1 day, 182 days  $\pm$  2 days, 196 days  $\pm$  2 days.
6. PK collection and/or safety bloodwork should be conducted for late visits, not unscheduled visits. PK collection and safety bloodwork may be performed during an unscheduled visit if it is within a participant's study visit window.
7. Vivitrol injection will be administered on Day 0 and on a monthly (28 days) basis afterwards days for a total of six injections. Study window for Vivitrol is  $\pm$  2 days, the earliest a participant can receive their next injection is two days before their scheduled visit, the latest they can receive it is two days after their study visit.

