#### 3.2 SECONDARY OBJECTIVES

- To confirm no accumulation between repeat doses
- To determine the safety and tolerability of Vivitrol over 196 days.

Safety endpoints will be captured throughout and will include the incidence of AEs including:

- deaths
- SAEs
- AEs leading to discontinuation
- common AEs
- AEs of special interest (injection site reactions and hepatic effects)
- laboratory abnormalities (absolute values and changes over time in laboratory parameters)
- the proportion of participants who discontinue treatment due to AEs)

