#### **7.3.3.4 Admission Day 140 to 142**

NTX blood samples (see section 7.2.4.1) will be collected at 140 days  $\pm$  1 day sample prior to Vivitrol re-administration. Participants will then be administered their sixth and final Vivitrol IM injection on Day 140 and the time recorded. NTX blood samples will be collected at 140 days +1 hr  $\pm$ 15 min, 140 days +2 hr  $\pm$ 15 min, 140 days +4 hr  $\pm$ 30 min, 140 days +8 hr  $\pm$  60 min, 140 days +12 hr  $\pm$ 60 min, 141 days  $\pm$  2 hr, 141.5 days  $\pm$ 2 hr, 141.75 days  $\pm$ 2 hr, 142 days  $\pm$ 2 hr under in-patient care. The actual time of each PK sample collection shall be recorded. Participants will then be discharged and provided with a timetable for their follow-

up visits, which will be carried out at Clinilabs.

Participants will also be monitored for AEs, concomitant medication review, Substance Use: Self report & UDS. Where applicable, a pregnancy test will also be conducted.

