#### **7.3.3.5 Vivitrol re-administration Day 28, 56, 84 & 112 ( $\pm 1$ day)**

There will be no intensive blood monitoring scheduled after administration of the 2nd, 3rd, 4th and 5th dose of Vivitrol as outlined in Table 7-1. In this instance, participants will be seen on an out-patient basis at Clinilabs for their re-administration of Vivitrol. Just prior to re-administration of Vivitrol, blood samples will be taken for: LFT, EUC & FBE; and NTX PK analysis to capture the Vivitrol trough level. The actual time of each PK sample collection shall be recorded relative to the re-administration of Vivitrol.

Participants will also be monitored for the following: AEs, PHQ-9, BDI-II, CSSRS, concomitant medication review, Vital signs, substance Use (Self report) and UDS. Where applicable a pregnancy test will also be conducted.

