## 8 ASSESSMENT OF SAFETY

### 8.1 SPECIFICATION OF SAFETY PARAMETERS

Safety will be assessed on the basis of:

- the incidence of death
- the incidence of SAEs
- the incidence AEs leading to discontinuation
- the incidence common AEs
- the incidence injection site reactions
- laboratory abnormalities indicating hepatic problems (absolute values and changes over time)

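### Table 7-1 schedules no liver panel from the sixth-dose admission until Day 196, so hepatic laboratory change is not sampled at the end of the sixth dosing interval

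*Combined protocol and SAP*

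**What the plan says.** Section 3.2 sets the objective "To determine the safety and tolerability of Vivitrol over 196 days" and lists among the safety endpoints "AEs of special interest (injection site reactions and hepatic effects". Section 8.1 repeats the laboratory part as "laboratory abnormalities indicating hepatic problems (absolute values and changes over time". Section 10.4.4 analyses laboratory safety by counting values outside the normal range.

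The schedule is in Table 7-1. The LFT/EUC/FBE column is marked at screening, at Days 28, 56, 84 and 112, at the Day 140-142 admission and at Day 196, and also at early termination and AE follow-up visits. It is blank at Day 143, in the row "Day 145, 147, 150, 154, 157, 161, 164, 168", and at Day 182. PK blood is drawn at all of those visits.

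The section text varies in how much it says. For the repeat doses on Days 28 to 112, Section 7.3.3.5 is explicit: "Just prior to re-administration of Vivitrol, blood samples will be taken for: LFT, EUC & FBE". For the sixth dose, Section 7.3.3.4 says "Participants will then be administered their sixth and final Vivitrol IM injection on Day 140 and the time recorded" and then "Participants will also be monitored for AEs, concomitant medication review, Substance Use: Self report & UDS", with no liver panel named. Section 7.3.5 refers to Table 7-1 for the final visit but gives its own list, also without a liver panel: "Participants will be monitored for the following: AEs, PHQ-9, BDI-II, CSSRS, concomitant medication review, Vital signs, substance Use (Self report) and UDS".

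**The concern.** Liver safety is singled out for special attention, and the laboratory endpoint is about change over time across repeated dosing. Yet dose 6, the last and the longest cumulative exposure, is the only dose with no scheduled panel near the end of its 28-day interval. The first value certain to come after it is taken at twice that distance.

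This matters because of the kind of event the protocol itself expects. Its hepatotoxicity warning (Section 2.3.1, item 4) describes transaminase rises that were short-lived and caused no symptoms. Only a blood test finds such a rise, and it may be gone by Day 196. If so, it would not enter the out-of-range counts of Section 10.4.4. Nor would it trigger the AE follow-up visit of Section 7.3.8, which depends on what is ongoing or abnormal at the last on-study visit.

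**Working it through.** **1. Interval from each dose to its next panel.** Dose days come from the study schematic (Section VI) and panel days from Table 7-1.

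| Dose | Given on Day | Panel on Day | Days after dose |
|---|---|---|---|
| 1 | 0 | 28 | 28 - 0 = 28 |
| 2 | 28 | 56 | 56 - 28 = 28 |
| 3 | 56 | 84 | 84 - 56 = 28 |
| 4 | 84 | 112 | 112 - 84 = 28 |
| 5 | 112 | 140-142 | 28 to 30 |
| 6 | 140 | 196 | 196 - 140 = 56 |

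Section 7.3.3.5 fixes the panels for doses 1 to 4 as pre-dose samples. For the Day 140-142 admission the table does not give the day of the draw or its timing relative to dose 6. If it is taken before the dose, dose 5 has a 28-day value and dose 6 has nothing until Day 196. If it is taken after the dose, dose 6 has a value within its first two days and again nothing until Day 196.

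**2. Effect of the windows.** The injection window is ±2 days (footnote 7 to Table 7-1) and the Day 196 window is ±2 days. The shortest gap is (196 - 2) - (140 + 2) = 52 days, and the longest is (196 + 2) - (140 - 2) = 60 days. The nominal gap from panel to panel is 196 - 142 = 54 to 196 - 140 = 56 days.

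**3. Visits inside the gap.** Day 143 (1), Days 145 to 168 (8) and Day 182 (1) make 10 visits with a PK draw and no liver panel. Day 168 is 168 - 140 = 28 days after dose 6, which matches the timing for the earlier doses.

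**4. The plan's own panel count.** Section 7.2.3 states 18 panels of 9.5 mL, totalling 180.5 mL. This does not reproduce:

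- 18 × 9.5 = 171.0 mL, whereas 180.5 / 9.5 = 19 panels.
- Table 7-1 gives 1 (screening) + 4 (Days 28 to 112) + 1 (admission) + 1 (Day 196) = 7 panels, or 7 × 9.5 = 66.5 mL.
- Drawing on each of Days 140, 141 and 142 gives 9 panels (85.5 mL). Adding early termination and AE follow-up gives 11.

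As a control, the PK count does reproduce: the list in footnote 5 plus the Day 0 pre-dose sample is 43 samples, and 43 × 9 = 387 mL as stated. The safety-panel count is therefore the outlier. The section's total is also off: 180.5 + 4 + 387 = 571.5 mL, against about 581.5 mL stated.

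**The case against.** The strongest reply is that the objective is measured. Day 196 follows all six doses and closes the 196-day period, AEs are monitored at Day 143, Days 145-168 and Day 182, and early termination carries a panel. The plan includes no dose-by-dose hepatic comparison. Section 4.1 expects no accumulation, so nothing presumes higher exposure at dose 6 than at dose 5. Most of this stands, and it limits the point to the sixth interval. AE monitoring does not close that gap, because it cannot detect a rise without symptoms. Footnote 6 allows safety bloods at late visits and some unscheduled ones but schedules none.

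A second reply is that 18 or 19 budgeted panels imply that more are intended. Adding Day 0, Day 143, the eight visits of Days 145-168 and Day 182 to the seven would give 7 + 1 + 1 + 8 + 1 = 18. The plan makes no such allocation, however, and the table leaves those cells blank. The surplus neither fills the gap nor rules out that it was meant to. For the same reason it cannot be used to show that an extra panel is already budgeted.

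A reader of Sections 7.3.3.4 and 7.3.5 might infer that the last panel is on Day 112. That goes too far. Section 7.3.5 defers to Table 7-1, which marks Day 196, and the list in Section 7.3.3.4 also omits vital signs and the mood scales that the table marks. This is a mismatch to correct, not a cancelled panel.

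**Conclusion.** The point holds in a limited form. Table 7-1 schedules no liver panel between the sixth-dose admission and Day 196, 56 days after dose 6 (52 to 60 with windows), against about 28 days for the other five doses. Hepatic laboratory change is not sampled within the sixth dosing interval, apart from a possible draw during the admission. A transient, symptomless rise after dose 6 could resolve before it is seen.

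This rests on Table 7-1 being the operative schedule, and on the unallocated panels of Section 7.2.3 not being meant for these visits.

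Three stronger inferences are not supported:

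- That liver safety goes unmeasured at full six-dose exposure. Day 196 measures it, though late.
- That Day 196 follows 28 drug-free days. No dose is given after Day 140, but the documents do not say that drug is absent after Day 168, and PK is still sampled on Days 182 and 196.
- That the hepatic profile will look cleaner than it is. It could, but no figure in the documents gives the direction or the size.

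**What to change.** 1. In Table 7-1, mark LFT/EUC/FBE at Day 168, drawn with the PK sample already scheduled. This means separating Day 168 from the shared Day 145-168 row or adding a footnote.
2. State that the Day 140 panel is drawn before the sixth dose. All six doses then have a panel at about 28 days.
3. Add the Day 140 and Day 196 panels to the lists in Sections 7.3.3.4 and 7.3.5, so that text and table agree.
4. Reconcile Section 7.2.3 with Table 7-1: 18 panels stated, a volume equal to 19, and 7 scheduled (8 after this change, 8 × 9.5 = 76.0 mL). Correct the overall blood total at the same time.

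The cost is one 9.5 mL panel per participant at an existing visit, so at most 15 extra panels, plus text edits. The change concerns only when the endpoint is measured and leaves dosing and the removal criteria untouched. Its limit is that a Day 168 panel would still miss a rise that resolves before Day 168.
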